Primary Outcome – The primary endpoint (outcome variable) is “*time to progression to incident diabetes.*” For most participants, incident diabetes will be diagnosed at one of the regularly scheduled study visits, which will occur every 6 months. In some cases, however, participants will notify study personnel that they have received a diagnosis of diabetes, or been placed on diabetes medication, by their personal physician. In such cases, every effort will be made to assess whether the participant has met the study criteria for incident diabetes. When participants have been placed on a diabetes medication and the diagnosis cannot be confirmed by D2d laboratory criteria or adjudicated by the clinical outcomes committee, the participant will be considered to have not reached the primary study

outcome and follow-up for incident diabetes will continue per the-intent-to treat principle. Sensitivity analyses will be performed that include these occurrences (i.e., a diabetes-specific medication is prescribed but a D2d-diagnosis of diabetes is not made) as cases of incident diabetes.

Statistical Methods - Since the exact time of progression to incident diabetes, defined as the date on which the criteria for incident diabetes would have been met if laboratory tests had been performed, will be unknown for participants who receive a diagnosis of incident diabetes at a regularly scheduled study visit, one could consider statistical methods for interval-censored data for the analysis of the time-to-event variables.²⁷⁷ However, subjects whose diagnosis is initiated by their personal physician will not have a diagnosis date corresponding to a regular visit, and participants will have variable visit schedules. Thus, we have chosen instead to use standard methods for analysis of right-censored time-to-event data, using the incidence date defined in Section 9.1 for the primary outcome. The interval-censored approach and the right-censored time-to-event approach would give similar estimates and standard errors for treatment effects, because the change in approach would have similar effects on the estimated time-to-event distributions in the two treatment groups. Moreover, the notion that each individual participant has a true exact date of onset of diabetes is a somewhat artificial concept, in that an individual will not consistently meet the diagnostic criteria on successive days as they transition from pre-diabetes to incident diabetes.

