4 PRIMARY ANALYSIS & SUPPORTING ANALYSES

The *primary analysis* of D2d will assess whether, in participants with pre-diabetes, oral daily vitamin D₃ supplementation reduces the rate of progression from pre-diabetes to incident diabetes (=primary outcome).

All randomized participants are included in the analysis. Kaplan-Meier estimates of “time to confirmed diabetes” distributions will be calculated for each treatment group. The log-rank test will then be used to perform an unadjusted comparison of the time-to-event distributions in the two treatment groups. Follow-up of participants who do not complete the study (e.g. withdrew) will be "censored" on the date of their last follow-up encounter (see below). Cox proportional hazard modeling will be used to compare the risk of incident diabetes in the two groups.¹ The model will include an indicator for the randomized intervention as its main predictor variable. Clinical site at randomization will be a stratifying factor. The baseline variables (BMI, race, as entered in SPIRS) used to stratify the randomization will also be included as stratifying factors.

The p-value from the primary analysis will be based on the chi-square statistic from a likelihood ratio test obtained from proportional hazards models with and without the term for intervention arm. Comparisons of the intervention groups will be performed per the ITT principle, with all randomized participants grouped per their intervention assignment at randomization, regardless of adherence. Unless otherwise specified, p values will be two tailed, and values below 0.05 are considered statistically significant.

Definitions of follow-up time and censoring. Follow-up time for the primary outcome will be censored at the date of the *last assessment for diabetes with data in the electronic data capture system as of the cutoff date (as defined in the Manual of Procedures – section 20)*.

Censoring for participants *with diabetes* occurs at the date of the diabetes event, as shown in the *Diabetes Outcome* form in EDC. Specifically,

- If the diagnosis of diabetes is made within the study (i.e., using results by the Central Laboratory), the date of onset of diabetes is defined as the date of the first diagnostic glycemc value.
- If the diagnosis of diabetes is made outside of study (i.e., adjudicated), the date of onset of diabetes is determined during the adjudication process.

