Censoring for participants *free of diabetes* occurs at one of the following dates:

- Death or active withdrawal.
- Last encounter *free of diabetes*, using the most recent of the following 3 options:
 - Scheduled encounter
 - Semi-annual visit (*or non-visit contact*)
 - Annual visit (*or non-visit contact*)
 - Interim phone call
 - Unscheduled visit to evaluate for diabetes in between semi-annual/annual visits [as described in Manual of Procedures – section 18].
 - Adjudicated event (that did not confirm diabetes).

Sensitivity analysis of the primary analysis

Competing event of diabetes medication use

The use of a diabetes medication (e.g., metformin for worsening pre-diabetes or for new diabetes diagnosed outside of D2d) is considered a “competing event.” Specifically, if vitamin D supplementation is presumed to be effective at reducing diabetes risk, more participants in the placebo group will be placed on a diabetes medication (e.g., metformin) for worsening pre-diabetes or early stage diabetes. If these participants do not meet the D2d criteria (i.e., by central laboratory criteria or adjudication) when starting a diabetes medication, they continue to be followed for incident diabetes within D2d, per ITT analyses. However, *the use of a diabetes medication in these participants practically removes them from the potential pool of those likely to meet the incident diabetes endpoint as the diabetes medication will improve glycemia. Such competing events reduce the power of the trial by lowering diabetes risk.* Importantly, because starting on a diabetes medication is more likely to occur in the placebo group – if the underlying hypothesis holds – these events falsely change the relative risk reduction towards null. Cases in which a diabetes medication has been started without the participant meeting the D2d criteria for diabetes are not uncommon because of local clinical practice or laboratory variability between the central D2d laboratory and local laboratories.

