To examine the potential effect of these “competing events” on study fidelity, *in sensitivity analyses*, the primary endpoint will be defined as “*time to incidence diabetes by D2d criteria or use of a diabetes-specific medication.*” This analysis includes participants that started and remained for more than 31 days on a diabetes-specific medication (for worsening glycemia, for weight loss or for any other reason) but the D2d criterion of incident diabetes was not made (by central laboratory criteria or adjudication). In this analysis, follow-up of participants for the primary outcome is censored at the time when the diabetes-specific medication begun.

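### Does the SAP's sensitivity analysis for diabetes-medication use code medication starters as non-events?

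*SAP*

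**What the plan says.** SAP Section 4, under the heading on the competing event of diabetes medication use, first explains the problem. Participants who start a diabetes drug without meeting the trial's criteria stay in the primary analysis: "they continue to be followed for incident diabetes within D2d, per ITT analyses". Because the drug lowers their glucose and, if vitamin D works, more of them will be on placebo, the SAP says that "these events falsely change the relative risk reduction towards null".

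The remedy is a sensitivity analysis with a redefined endpoint, "time to incidence diabetes by D2d criteria or use of a diabetes-specific medication". Its population is described next: "This analysis includes participants that started and remained for more than 31 days on a diabetes-specific medication", for any reason, where no trial diagnosis was made. The last sentence then says that "follow-up of participants for the primary outcome is censored at the time when the diabetes-specific medication begun".

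Earlier in Section 4, the paragraph defining follow-up time and censoring states that censoring for participants with diabetes "occurs at the date of the diabetes event". In the description of the primary analysis, the sentence beginning "Follow-up of participants who do not complete the study (e.g. withdrew) will be" goes on to censor those participants at their last encounter.

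Protocol Section 11.2 deals with participants who were put on a diabetes drug without a confirmed diagnosis: "Sensitivity analyses will be performed that include these occurrences", with these counted as incident diabetes. Protocol Section 9.1, on adjudication, says the same.

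**The concern.** In ordinary survival-analysis vocabulary a censored observation carries status 0. Taken literally, the closing sentence assigns a non-event to every participant who started a diabetes drug without a trial diagnosis. The definition two sentences before it makes the same occurrence an event.

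If a programmer followed the literal reading, the medication half of the endpoint would contribute nothing. Any trial diagnosis made after the drug was started would also be lost, because it falls after the censoring date. The analysis could then not show whether unconfirmed medication starts pull the treatment effect toward the null, which is its purpose. The SAP remarks that such starts are not rare, so the two codings would be expected to give different answers.

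**Working it through.** **Step 1. What each text implies for a participant on a diabetes drug for more than 31 days with no trial diagnosis.**

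| Text | Implied status |
|---|---|
| SAP 4, sensitivity endpoint: "time to incidence diabetes by D2d criteria or use of a diabetes-specific medication" | Event |
| SAP 4, population: "This analysis includes participants that started and remained for more than 31 days on a diabetes-specific medication" | Event. Section 4 already puts all randomized participants in the analysis, so saying that these are included adds something only if they are included as events |
| SAP 4, purpose: "these events falsely change the relative risk reduction towards null" | Event. Leaving them uncounted is the stated problem |
| Protocol 9.1 and 11.2 | Event. Counted as diabetes cases in sensitivity analysis |
| SAP 4, closing sentence: "follow-up of participants for the primary outcome is censored at the time when the diabetes-specific medication begun" | Non-event if *censored* is strict; silent on status if it means that follow-up ends |

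**Step 2. Which meaning of *censored* does the SAP use?** Both. The rule for non-completers is strict. The rule for participants with diabetes, that censoring "occurs at the date of the diabetes event", cannot be: read strictly it would code every primary event as a non-event. In the paragraph that defines follow-up time, the word therefore means that the clock stops, and status comes from the endpoint. Read that way, the closing sentence supplies the date that the endpoint definition lacks, and nothing conflicts.

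**Step 3. Bounds that need no rate.** Let E be the number of events in the primary analysis.

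- Starters as events: everyone with a trial diagnosis still has an event, at diagnosis or earlier at the drug start, and medication-only participants are added. Events ≥ E.
- Starters as non-events: medication-only participants add 0, and diagnoses after the drug start are lost. Events ≤ E.

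**Step 4. Illustration of size.** The documents give no medication-start rate, so the rates below are assumptions. The other inputs are from Protocol Section 11.1: 2,382 randomized, so 1,191 per arm; placebo diabetes hazard 0.1054; hazard ratio 0.75, so 0.1054 × 0.75 = 0.07905 on vitamin D; loss hazard μ = 0.0513; uniform accrual over 2 years and 4 years in total, so follow-up t is uniform on 2 to 4 years.

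The protocol's event target is reproduced by Schoenfeld's formula: 4 × (1.960 + 1.282)² / (ln 0.75)² = 508.

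With diabetes hazard λ and medication-start hazard γ, the expected number of occurrences of a type with hazard h in one arm is

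1,191 × average over t of [h / (λ + γ + μ)] × [1 − exp(−(λ + γ + μ)t)].

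With γ = 0 this gives 298.4 + 232.4 = 531 events at hazard ratio 0.75 (protocol: 521) and 597 under the null (protocol: 586). Both are within 2%.

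Coded as events, the composite hazard ratio is (0.07905 + γ₁) / (0.1054 + γ₀), where γ₀ is the placebo start hazard and γ₁ the vitamin D start hazard. For γ₀ = 0.02 and γ₁ = 0.01 it is 0.08905 / 0.1254 = 0.71. All starters are taken to stay on the drug for more than 31 days.

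| γ₀ per year | γ₁/γ₀ | Starters as events: events, HR | Starters as non-events: events, HR |
|---|---|---|---|
| 0.005 | 1.0 | 556, 0.761 | 527, 0.75 |
| 0.005 | 0.5 | 549, 0.739 | 528, 0.75 |
| 0.02 | 1.0 | 628, 0.790 | 516, 0.75 |
| 0.02 | 0.5 | 603, 0.710 | 519, 0.75 |
| 0.03 | 1.0 | 675, 0.805 | 509, 0.75 |
| 0.03 | 0.5 | 638, 0.695 | 514, 0.75 |

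The coding would matter if it were open. Steps 1 and 2 show that it is not.

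**The case for a change.** The strongest case for a change is that the SAP's looser use of the word is confined to participants who have diabetes, whereas these participants have no trial diagnosis. On the SAP's own split they belong with those free of diabetes. Every date listed for that group is a non-event, including an adjudication that did not confirm diabetes, which describes some of these starters. The SAP also calls medication use a competing event, and competing events are often censored. The 31-day rule appears only in the sensitivity analysis in the SAP, not in the matching protocol text, so a programmer might hesitate to let the protocol override an explicit SAP sentence.

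Some of this stands: the word is badly chosen, and the literal reading would empty the analysis. The rest does not carry. The list for participants free of diabetes serves the primary endpoint and has no entry for starting a drug; in the primary analysis these participants are kept under follow-up. Under the redefined endpoint they are no longer free of the event. The competing-event label introduces a complaint that such participants go uncounted, and the wider endpoint is the answer to it. The protocol need not override the SAP, because the SAP's endpoint definition already agrees with it.

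One small point remains: a participant who starts a drug and is diagnosed later. That person has an event either way, and a time-to-first reading of the two-part endpoint dates it at the drug start, as the closing sentence does.

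**Conclusion.** No change follows. The closing sentence uses *censored* to mean that follow-up ends, as the SAP does for confirmed diabetes cases. The endpoint definition, the stated purpose and two protocol sections make a qualifying medication start an event on the date the drug was begun. An analyst working from the documents would code it that way, so spelling out the status would record what is already implied and alter no result.

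The choice between codings is not trivial in itself: in the illustration it separates 549 to 675 events from 509 to 528. That range rests on assumed start hazards of 0.005 to 0.03 per year on placebo and vitamin D to placebo ratios of 0.5 to 1.0. The conclusion does not rest on those assumptions. It rests on reading the sentence together with the definition it follows. The matter is confined to one sensitivity analysis; the primary analysis, its p-value and the 508-event target are untouched.

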4.3 Heterogeneity of treatment effect (HTE) analyses in relation to the primary outcome

4.3.1 Subgroup analyses

Heterogeneity of treatment effect to vitamin D supplementation for the primary outcome will be assessed in a standard approach by **subgroups** defined by the following **baseline** characteristics (i.e., at the time of randomization) will be conducted. The analysis plan follows widely recommended best practices: pre-specification of subgroups (motivated by biologically plausible hypotheses), interaction tests for heterogeneity of effects adjusted for multiple comparisons (see below), and inference for subgroup-specific effects only in the context of a statistically significant interaction.^{2-7 8,9}

- ✓ In general, subgroup analyses - even when pre-specified - are considered exploratory, as the power to detect heterogeneity of effects is generally low. Nevertheless, to adjust for multiple comparisons, we will use the Hochberg Sequential procedure¹⁰ when evaluating the significance (p-value for the interaction term) of each subgroup analysis. This procedure uses progressively more stringent statistical thresholds and is less rigid than the traditional Bonferroni correction method.
- Blood 25OHD concentration by a key Institute of Medicine cutoff (ng/mL) [justification: risk reduction will be larger among those with 25OHD < 20 ng/mL]
 - b. < 20
 - c. ≥ 20
- Race by self-reported definitions [justification: risk reduction will be larger among Blacks]
 - a. White
 - b. Black/African American
 - c. Other
- Glycemic risk by pre-diabetes criteria [justification: risk reduction will be larger among those who meet all three criteria and are considered at higher risk for diabetes]
 - a. Three criteria (FPG, A1c and 2hPG)
 - b. Two criteria (all other participants: FPG/A1c, FPG/2hPG, A1c/2hPG)
- BMI by standard clinical categories based on BMI (kg/m²) [justification: risk reduction will be larger among those with higher BMI]
 - a. Normal weight / Overweight < 30
 - b. Obese ≥ 30
- Glycemic risk by meeting 2hPG criterion for pre-diabetes [justification: differences in the underlying pathophysiology of people diagnosed by 2hPG may be important for the effect of vitamin D]
 - a. 2hPG (FPG/2hPG, A1c/2hPG, FPG/A1c/2hPG)
 - b. FPG/A1c only
- Ethnicity
 - a. Hispanic
 - b. Non-Hispanic
- Sex
 - a. Men
 - b. Women
- Waist circumference
 - a. < median value
 - b. ≥ median value

- Age
 - a. < median value
 - b. ≥ median value
- Geographic location as a proxy for sun exposure
 - a. above 37° latitude
 - b. below 37° latitude
- Calcium intake [to test for potential interaction]
 - a. < median value
 - b. ≥ median value

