4. STUDY DESIGN, INTERVENTION AND PROCEDURES

4.1 Overview of Study Design

The D2d study is a multicenter, randomized (1:1), double-masked, placebo-controlled, parallel-group primary prevention clinical trial with 2 arms (oral daily vitamin D₃ vs. placebo) in participants at high risk for diabetes (with pre-diabetes) who will be followed for approximately 4 years after randomization for incident diabetes (Figure 4.1).

Adults at increased risk for type 2 diabetes (*pre-diabetes*), defined as meeting two-out-of-three ADA glyceic criteria established in 2010 (FPG 100-125 mg/dL or 2hPG 140-199 mg/dL or HbA1c 5.7-6.4%), will be randomized to receive, once daily, either a single soft-gel of vitamin D₃ (cholecalciferol, 4,000 IU) or matching placebo. Study participants will be seen every 3 months during the first 6 months and every 6 months for the remainder of the study. At the midpoint of each 6-month interval after the month 6 visit, participants will receive a telephone call to encourage compliance, assess for adverse events and receive a reminder of their upcoming visit. The primary outcome will be *time to diabetes*, defined by laboratory criteria derived from a 75-gram OGTT [to obtain 2hPG] done annually, FPG and HbA1c done every 6 months or when symptoms consistent with hyperglycemia are reported (Figure 9.1).

Figure 4.1. Schematic of Study Design

¹ Two out of 3 glyceic criteria are met: FPG 100-125 mg/dL (5.5-6.9 mmol/L); HbA1c 5.7-6.4% (39-46 mmol/mol); 2hrPG 140-199 mg/dL (7.7-11.0 mmol/L)

² Mean follow-up is estimated to be approximately 3 years. Because D2d is an event-driven trial, follow-up period is an estimate

³ Based on laboratory criteria: 1 out of 3 glyceic criteria are met: FPG ≥126 mg/dL (7 mmol/L); HbA1c ≥6.5% (47.5 mmol/mol); 2hrPG ≥200mg/dL (11.1 mmol/L)

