Rationale for chosen age range. The study will include participants equal to or older than 30 years (≥25 years for people of the following high-risk races: American-Indian, Alaska Native, Native Hawaiian or Other Pacific Islander). Risk for pre-diabetes increases with age but we chose a lower age than what is typically considered higher risk (>45 years), because lower age at diagnosis of pre-diabetes is associated with higher progression to diabetes.⁵ Also, this age cutoff would reduce “contamination” with type 1 diabetes or Latent Autoimmune Diabetes of Adults and minimize loss to follow-up due to social mobility. The planning committee selected no upper age limit to increase the generalizability of findings and to allow for heterogeneity of treatment effect (subgroup) analyses by age.

Rationale for chosen weight/body mass index range. The study will include participants with a BMI equal to or higher than 24 (22.5 kg/m² for Asians) but not higher than 42 kg/m² because overweight/obesity is a significant risk factor for type 2 diabetes and because those with severe obesity require much higher doses of vitamin D to achieve the desired 25OHD concentration.²³⁸

Rationale for lack of “low vitamin D status” as an inclusion criterion: Vitamin D status (assessed by blood 25OHD concentration) at baseline is not an inclusion criterion for the following reasons: (1) in small trials, vitamin D benefited those with pre-diabetes irrespective of baseline 25OHD concentration;^{19,24} (2) the definition of ‘optimal’ vitamin D status is controversial and no consensus exists on optimal blood 25OHD level,^{172,176,185,239-243} (3) suboptimal vitamin D status is widespread in the U.S. adult population, especially among overweight and obese persons,^{49,198,244-250} (4) to ensure that the study is as “pragmatic” as possible and results are generalizable to clinical practice,²⁵¹ (5) baseline 25OHD is a treatment selection marker to enter the heterogeneity of treatment effect (subgroup) analyses and to assess its performance, participants with a wide range of 25OHD must be enrolled;²⁵² (6) 25OHD concentration varies by season,^{185,253} and may decrease during acute phase response,^{254,255} (7) screening with 25OHD would be cumbersome and expensive. All participants will be encouraged to take the IOM recommended dose of vitamin D for their age.

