11. SAMPLE SIZE CALCULATIONS AND DATA ANALYSIS

11.1 Sample Size Calculation (Power Analysis)

The primary aim of D2d is to assess whether, in participants at risk for diabetes, oral daily vitamin D₃ supplementation will reduce the rate of progression to incident diabetes when compared to placebo.

The D2d study is designed as an event-driven trial to assure that the intended power to detect the hypothesized treatment effect (hazard ratio = 0.75, see below) is achieved irrespective of the event rate in the placebo arm.

The following considerations were used to determine the required number of events:

- 1) The primary study outcome is “time to confirmed diabetes”.
- 2) The primary hypothesis will be tested at a two-sided type 1 error rate (alpha) of 0.05.
- 3) If vitamin D therapy is superior to placebo, the hazard ratio will be 0.75 in the vitamin D arm as compared to the placebo arm.
- 4) The study is designed to have power of 90% to detect a hazard ratio of 0.75.

Based on these assumptions, the required number of events is 508²⁶⁴. To achieve the intended power, D2d will continue until 508 primary events have occurred.

Based on the following assumptions, it is estimated that the required (i.e. randomized) sample size will be 2,382 participants.

- 5) Participants will be recruited over a 2-year period (“accrual period”)
- 6) The expected study duration will be approximately 4 years plus an end-of-study visit over a period not to exceed three months.
- 7) The incidence rate of confirmed diabetes will be 10% per year (hazard rate = 0.1054) in the placebo group.
- 8) The loss-to-follow-up (i.e. going “off study”) rate will be up to 5% per year of follow-up (hazard rate = .0513).
- 9) If vitamin D therapy is superior to placebo, the hazard ratio will be 0.75 in the vitamin D arm as compared to the placebo group.

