There are two observational studies of particular importance and relevance to the D2d study that were not included in the above meta-analyses: In the DPP study, among participants with pre-diabetes, there was an inverse linear association between 25OHD and incident diabetes, after multivariate adjustment including change in BMI and physical activity, with the hazard ratio for incident diabetes being lowest (0.46; 95%CI, 0.23 to 0.90) in the highest category (25OHD \geq 50 ng/mL) compared to the lowest category (25OHD $<$ 12 ng/mL) with no evidence of a threshold.²⁵ In another observational study, progression from pre-diabetes to type 2 diabetes was reduced by 73% among those with 25OHD $>$ 28 ng/mL compared to those with 25OHD $<$ 18 ng/mL.¹⁹⁵

Intervention studies: In the CaDDM trial, 2,000 IU/day of vitamin D₃ supplementation, which raised 25OHD to 31 ng/mL, improved measures of beta cell function (disposition index) by ~40% and glycemia (HbA1c) by ~50% after 4 months.²⁴

After taking into consideration all published data and short-term mechanistic studies on vitamin D and diabetes, a hazard ratio of 0.75 (i.e. 25% reduction in risk in the intervention arm) was used as the assumed treatment effect in sample size calculations. A reduction of this magnitude would clearly be clinically significant to public health.

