Subgroup Analyses - Variability of response to vitamin D supplementation will be assessed by pre-specified analyses in participant subgroups defined by *baseline* variables, e.g., race (self-reported definitions of White, vs. non-White e.g. Black/African American, American Indian, Alaska Native); ethnicity (Hispanic vs. Non-Hispanic); BMI (two groups based on median value); waist circumference (two groups based on median value);¹⁸⁷ age (two groups based on median value); geographic location (two groups, above or below 42° latitude), calcium intake and 25OHD concentration (two groups based on median value). Subgroup analyses by clinically applicable cutoffs will also be done (e.g. BMI as normal weight, overweight or obese; 25OHD concentration by IOM cutoffs). Each analysis of participant subgroups will include a test for interaction. Effect modification will be claimed only if the test for interaction reaches statistical significance. These analyses, although pre-specified, are considered exploratory as the study is not powered for such analyses and multiple comparisons must be considered when interpreting findings that are nominally statistically significant. We will also assess variability of response to vitamin D supplementation by “per-protocol” and “on-treatment” analyses, where treatment is defined by adherence based on pill count or achieved 25OHD concentration. These analyses will also be considered to be exploratory.

Missing Data - Missing data are inevitable in clinical research. Every effort will be made to minimize missing data in D2d. The primary methods of data analysis assume that censoring for time-to-event variables is non-informative. However, as recommended in the recent report of the Institute of

Medicine, we will perform sensitivity analyses to assess the degree to which the results are sensitive to the validity of the assumptions of non-informative censoring or non-informative missingness.

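### SAP 4.3.1 tests six continuous effect modifiers only as two groups; a graded interaction would be tested with appreciably less power than the data allow

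*SAP*

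**What the plan says.** SAP 4.3.1 defines subgroups on eleven baseline characteristics. Each gets an interaction test, the interaction p-values are adjusted by the Hochberg procedure, and subgroup-specific effects are interpreted only where the interaction is significant. The same section calls these analyses exploratory and says their power is generally low.

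Six of the eleven are numeric measures reduced to two groups:

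- **25OHD**, described as "Blood 25OHD concentration by a key Institute of Medicine cutoff (ng/mL" units, below 20 against 20 and above. The stated hypothesis is a larger risk reduction below 20.
- **BMI**, below 30 against 30 and above, with a larger risk reduction expected at higher BMI.
- **Waist circumference, age and calcium intake**, each split at the median. No reason is given for expecting the effect to change there.
- **Latitude**, with one group "above 37° latitude" and the other below it.

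Protocol 11.2 also works in categories: mostly median splits, latitude "above or below 42° latitude", and further clinical cutoffs (three BMI groups, IOM cutoffs for 25OHD). No treatment-by-continuous-modifier term appears in either document.

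Protocol 4.3.8 gives, as one reason for not selecting on vitamin D status, that baseline 25OHD is to be assessed as a treatment-selection marker, for which "participants with a wide range of 25OHD must be enrolled".

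**The concern.** Cutting a continuous modifier in two treats everyone on one side of the cut as alike. If the treatment effect changes gradually with the modifier, the two-group interaction test uses only part of the information collected. The SAP already concedes low power and makes a significant interaction the condition for interpreting subgroup effects. An avoidable loss of power at that step therefore makes it more likely that a real gradient is missed.

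The case is clearest for waist, age and calcium intake. A sample median has no biological meaning, and the SAP offers no reason for a jump there. For 25OHD the protocol deliberately enrolled a wide range, and the planned test uses only the side of 20 ng/mL on which a participant falls.

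**Working it through.** **Inputs.** Protocol 11.1: "The primary hypothesis will be tested at a two-sided type 1 error rate (alpha) of 0.05"; "The study is designed to have power of 90% to detect a hazard ratio of 0.75"; 508 events. Protocol 4.1: 1:1 allocation. SAP 4.3.1: eleven modifiers, so the strictest Hochberg step is 0.05/11 = 0.0045. The documents give no modifier distributions and no interaction sizes, so those below are assumptions.

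**Plan's own figure.** Schoenfeld events = 4 × (1.960 + 1.282)² / (ln 0.75)² = 507.8, rounded up to 508. The stated figure is reproduced. The plan states no interaction power.

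**Information kept by a split.** For a linear interaction, the efficiency of the two-group test relative to the linear term is corr(X, indicator)². For a normal X with a share p below the cut c this is φ(c)² / [p(1 − p)]. At the median it is 2/π = 0.637, a loss of 36.3%. On that basis 508 events do the work of about 508 × 0.637 = 323.

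**Other shapes and cuts (all assumed).**

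| Modifier distribution and cut | Information lost |
|---|---|
| Normal, 50/50 | 36% |
| Normal, 40/60 | 38% |
| Normal, 30/70 | 42% |
| Normal, 20/80 | 51% |
| Uniform, median | 25% |
| Lognormal, log SD 0.3 to 0.7, median | 41% to 58% |
| Two illustrative site-latitude patterns, cut at 37° | 12% and 16% |

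Protocol 4.3.1.2 expects a mean baseline 25OHD of about 20 ng/mL, so that cut should fall near the centre. For BMI, eligibility truncates the range at 24 (22.5 for Asians) to 42 and the share below 30 is not stated. The lognormal rows may suit calcium intake. They assume an interaction linear on the raw scale; if it is linear in the logarithm, the loss returns to 36%.

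**Power with 508 events, normal modifier, median split.** The SE of the interaction per SD is 2/√508 = 0.0887. The two halves differ by 2√(2/π) = 1.596 SD on average, and the SE of their contrast is 4/√508 = 0.1775. Power = Φ(effect/SE − z), with z = 1.960 at 0.05 and 2.838 at 0.05/11.

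| Assumed log-HR per SD | HRs in the two halves, centred on 0.75 | Alpha 0.05: linear vs split | Alpha 0.05/11: linear vs split |
|---|---|---|---|
| 0.15 | 0.67, 0.85 | 39% vs 27% | 13% vs 7% |
| 0.25 | 0.61, 0.92 | 80% vs 61% | 49% vs 28% |
| 0.30 | 0.59, 0.95 | 92% vs 77% | 71% vs 44% |

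**The reverse case.** Suppose the effect is a step at the median with a ratio of HRs of 1.49. The split gives z = ln 1.49 / 0.1775 = 2.25 and power 61%. The linear term has z = 2.25 × √0.637 = 1.79 and power 43%.

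**The case against.** The strongest reply is that two of the cuts are deliberate. The 25OHD contrast matches a hypothesis stated in terms of 20 ng/mL, and as the reverse case shows, the split is the better test of a step there. BMI below or above 30 is a randomization stratum (protocol 7.3.1) and a stratifying factor in the primary Cox model (SAP section 4). Both points stand, and both contrasts should remain as planned tests.

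Other parts of the reply also hold:

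- A reader might take the protocol's report of a relation between 25OHD and diabetes "with no evidence of a threshold" (section 11.1.2) as evidence for a linear interaction. It is not. That is an observational association with incidence. If log-hazard is linear in 25OHD and supplementation raises everyone's level by a similar amount, the expected interaction with baseline is zero.
- Enrolling a wide range of 25OHD is compatible with a two-group comparison; it does not oblige a continuous one.
- A reader might apply 36% to all six modifiers. It needs approximate normality, a linear interaction and a near-central cut. Latitude, a clustered site-level quantity, does not meet those conditions, and BMI is not shown to.
- A reader might conclude that the cuts decide whether the trial can say anything about who benefits. Both documents label these analyses exploratory, and for a modest interaction (0.15 per SD) neither test has useful power.
- The move from 42 to 37 degrees without a stated reason is a separate documentation point. It lends no support to the information loss.

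What the reply does not answer is the median split of waist, age and calcium intake, or the absence of any test that would detect a gradient efficiently.

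**Conclusion.** The point holds in a limited form. Six numeric modifiers are tested only as two groups, and no continuous interaction is planned. The loss is about 36% of the interaction information where the modifier is roughly normal, the cut is near its median and the interaction is linear, and about 12% to 58% under the other shapes and cuts tried. For interactions of 0.25 to 0.30 log-HR per SD, that means roughly 15 to 19 percentage points of power at alpha 0.05 and 21 to 27 (from unrounded values) at the strictest Hochberg step. These interaction sizes are assumed, and large: the hazard ratio would be near 0.6 in one half and above 0.9 in the other. The comparison reverses if the effect is a step at the cut.

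This is a worthwhile, inexpensive improvement to an exploratory analysis. It does not touch the primary analysis.

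**What to change.** Amend SAP 4.3.1 before unmasking:

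1. **Waist, age, calcium intake.** Take the interaction p-value that enters Hochberg from treatment × continuous baseline value (linear, with a spline as a shape check). State the scale in advance, especially for calcium intake if it is skewed. Keep the two halves for display. This is a substitution, so the family stays at eleven.
2. **25OHD and BMI.** Keep the contrasts at 20 ng/mL and 30 kg/m² as the Hochberg tests. Add a pre-specified, supportive treatment × continuous interaction for each, outside the Hochberg family.
3. **Latitude.** Leave it as a site-level grouping.

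The cost is a paragraph of SAP text and a few model terms, with no new data. The drawback is an assumed linear interaction in item 1, which would be less powerful than the split if the effect did step at the median; the spline is there to show a poor fit.
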